### **Risks to Participants**

Risks to Schizophrenia participants: The interviews, questionnaires, and neuropsychological tests present no significant physical, psychological, social, or legal risks are associated with involvement in the study. All measures are physically non-invasive, have been used in prior research, and elicit minimal distress or discomfort. The assessment tasks have been used in many other research studies with psychiatric patients. They are not harmful or unpleasant. Some participants may experience some embarrassment discussing personal information or when participating in the study interviews. The major costs to participants involve the time required to complete the assessments and to participate in the study interview as well as confidentiality and storage of data. The study interventions are low risk, psychosocial interventions. Participants will continue with their regular mental health treatment (both psychosocial and pharmacological) while engaged in the study and continue to receive care with their regular treatment team. To ensure continuity of care for study participants, we will maintain regular contact with participants' treatment teams to discuss serious issues that emerge during study participation such as medication side effects, recurrence of symptoms, and risk of self-harm or threats to others. The PI will provide supervision and consultation with study interventionists to address clinical issues, and will communicate with patients' treatment teams whenever necessary. These contacts will be described in the informed consent document so participants will be aware that study interventionists communicate with their treatment teams around serious clinical issues.

Risks to Mental Health Provider participants: Qualitative interviews regarding implementation of EnCoRE present no significant risks. Such interviews are not harmful or unpleasant. The major costs to participants involve the time required to participate in the study interview as well as confidentiality and storage of data.

### **Data Collection**

Schizophrenia Participants will complete baseline (BL; 180-240 minutes; \$30), post-treatment (PT; 120 minutes; \$30), and 3-month follow-up (FU, 120 minutes; \$30) assessments. All participants who are randomized will be contacted for all assessments (intent-to-treat) regardless of attendance at sessions. Assessments can be completed across multiple appointments if needed.

Three types of data will be collected: quantitative data, qualitative data, and interventionist tracking/logs. All measures have been used in research with individuals with schizophrenia and/or evaluation research and have good psychometric properties. We also will conduct qualitative interviews in order to examine feasibility and acceptability to inform future adoption, implementation and sustainability. First, Veterans who participated in EnCoRE will complete a 30-60 minute qualitative interview at post-treatment regarding aspects of EnCoRE they perceived as more or less helpful, interesting, and valuable. For example, we will ask how they liked the group format, what they found helpful, and what they would change, what the

study interventionist did well or could have done differently, and for any other reflections or suggestions about the intervention. Second, we will also conduct qualitative interviews with 20 mental health providers who work with Veterans with schizophrenia at the study sites. These interviews will solicit their experiences treating veterans with schizophrenia and negative symptoms and their impressions regarding EnCoRE content, processes, and how the program integrated with participants' other mental health care. Qualitative interviews will be conducted by the PI, [name] (Co-I), [name] and [name] (study coordinators), and [name] and [name] (research assistants) and will be audio recorded so that information can be summarized (see Data Analysis for further description of qualitative analyses). When both the Veteran and provider qualitative interviews are completed, the PI and Co-I will integrate themes, issues, and suggestions (see Data Analysis). Findings will be discussed among the investigators, and used to revise intervention materials to inform future implementation of EnCoRE. We will also gather information from EnCoRE interventionists. First, notes from all supervision meetings throughout the study will be kept and reviewed. Interventionists will be asked to describe their experiences in the individual and group EnCoRE sessions, the strengths and weaknesses of the program content in terms of delivery, and the topics/sessions that most resonated with Veterans. Second, interventionists will also keep logs of each individual and group session, recording information on the topic, the number of Veterans in attendance, observations, and what areas of content or group process appear to be more or less relevant and interesting to participants. These logs will be reviewed by the investigators throughout and at the end of the study to determine content for developing a draft implementation manual and other implementation results.

We have extensive experience tracking participants and expect to achieve an 80% follow-up rate. Data will be collected by experienced Research Assistants (RA) who will be trained using a library of videotaped assessments from our laboratory. All assessments will be supervised by the PI and co-Is. New interviewers will rate 4 videotaped interviews and demonstrate reliability on these instruments as reflected by Intraclass Correlation Coefficients (ICCs) of .80 or greater at the factor score level (continuous ratings), or Kappas greater than .80 (dichotomous ratings) prior to rating participants. Interviews will be videotaped to permit reliability checks [1 interview for every 5 completed (20%)]. Data will be coded by the RA who conducted the assessment and checked by a second RA. Discrepancies will be brought to the PI and resolved.

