## 3.0 Objectives

The goal of this study is to evaluate an innovative psychosocial intervention package that will incorporate evidence-based treatment strategies to target the affective-motivational

deficits, negative expectancies, and behavioral skills deficits that are central to the maintenance of negative symptoms. The intervention - called EnCoRE (Engaging in Community Roles and Experiences) - will include strategies aimed at teaching Veterans with schizophrenia and negative symptoms ways to (1) overcome deficits in anticipatory pleasure, (2) increase intrinsic motivation for goal-directed activities, (3) reduce expectancies for failure, and (4) perform skillfully in new social situations, all of which can impact implementation of new skills and behaviors. Rather than develop a new set of intervention strategies, we will include within EnCoRE evidence-based strategies for these treatment domains. In addition, we will collect qualitative information both from Veterans concerning their perceptions of the strengths, weaknesses, and barriers to participation in EnCoRE, as well as from a sample of mental health providers who work with Veterans with schizophrenia and negative symptoms, in order to inform a larger scale implementation trial should EnCoRE prove effective here.

Following a short pilot to train interventionists and refine the manual, we will conduct a randomized controlled trial to test the efficacy of EnCoRE in improving ratings of negative symptoms, functional outcomes, and engagement in community activities in a sample of Veterans with schizophrenia and negative symptoms (n=108). Participants will be randomized either to EnCoRE or a health-related control group. These goals fit well within the objectives of the RR&D program of funding research aimed at studying rehabilitation interventions focused on maximizing functional recovery and assisting in the integration of Veterans into civilian life. Specifically, we will address the following Specific Aims:

Specific Aim 1: Train therapists and refine the EnCoRE manual in a preliminary trial with 10 Veterans with schizophrenia and negative symptoms.

Specific Aim 2: Conduct a randomized controlled trial (n=108, medium effect, alpha=.05) to test the efficacy of EnCoRE in producing positive changes at post-treatment and 3-month follow-up on the primary outcomes of negative symptoms and social and community functioning.

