Specific Aim 3: Examine qualitative interviews completed by (1) Veterans who participated in EnCoRE and (2) Mental Health Providers to determine aspects of EnCoRE that were perceived as more or less helpful, interesting, and valuable in order to make adjustments prior to conducting a larger, multi-site implementation trial.

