Specific Aim 3: Examine qualitative interviews completed by (1) Veterans who participated in EnCoRE and (2) Mental Health Providers who work with Veterans with schizophrenia to determine aspects of EnCoRE that were perceived as more or less helpful, interesting, and valuable in order to make adjustments prior to conducting a larger, multi-site implementation trial. Qualitative data analyses will be organized and supervised by [name]. Interviews with Veterans randomized to EnCoRE (n=49) and mental health providers who work with Veterans with schizophrenia in PRRCs (n=10) will be audiotaped and transcribed by a trained HIPAA compliant professional. We will analyze data in 3 phases employing “constant comparison” of data units with others and data with emerging themes. Transcripts will be: (1) read and discussed by the PI and Co-I, creating a brief summary that captures our best understanding of what the interviewee sought to convey; (2) closely open-coded (categorizing each line or small unit of data with labels that convey their meaning vis-a-vis the study focus) by 2 team members, and these codes discussed to consensus. Breaking the data into small units and not using an a priori code template helps keep analysis focused on the data and the interviewee’s meaning, minimizing tendencies to see data through one’s preconceived ideas about the topics at hand; (3) As these steps near completion, we will examine meaning across interviews via focused cross-interview coding to organize themes, variations and interrelationships among the ideas, views, and experiences conveyed by the multiple interviews. We will pay particular attention to ideas/themes that can contribute to intervention effectiveness and implementation. In doing so we will consider interviewee’s personal reflections distinct from their observations/impressions of other Veterans, and will pay close attention to their personal theories regarding the nature, causes, structure, meaning, effects, and management of negative symptoms. Qualitative software program Atlas-ti 5.0 will be used. The study team will discuss the results to identify concrete ideas for improving/refining the intervention suggested by each point in the combined summaries. The results of (2) will also be used by the study team to identify issues related to feasibility and implementation.

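### The protocol allows the PI, who supervises the interventionists, to conduct the interviews that ask EnCoRE Veterans how their interventionist could have done better

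*Protocol*

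**What the plan says.** The relevant statements are spread over four parts of the protocol. The SAP covers only the quantitative outcomes and does not mention the interviews.

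- **Purpose.** Section 3.0 says that Veterans' views are sought on "perceptions of the strengths, weaknesses, and barriers to participation in EnCoRE". Specific Aim 3 is to "determine aspects of EnCoRE that were perceived as more or less helpful, interesting, and valuable in order to make adjustments" before a larger trial.
- **Who is interviewed, and about what.** Data Collection in section 5.1 says "Veterans who participated in EnCoRE will complete a 30-60 minute qualitative interview at post-treatment". The example questions cover the group format, what helped, what the Veteran would change, and what the "study interventionist did well or could have done differently".
- **Who interviews.** The same section says "Qualitative interviews will be conducted by the PI, [name] (Co-I", then lists two study coordinators and two research assistants. One list serves both the Veteran and the provider interviews.
- **Who supervises delivery.** Risks to Participants says "The PI will provide supervision and consultation with study interventionists to address clinical issues". No site or interventionist is excepted.
- **Who analyses.** Under Specific Aim 3 in section 5.6, transcripts are first "read and discussed by the PI and Co-I, creating a brief summary". Two team members then open-code them to consensus without a preset template. Data Collection has the PI and Co-I integrate the themes.

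**The concern.** A person asked to judge a service tends to be more generous when the listener is responsible for it. Here one of the permitted interviewers supervises the individual whose performance is being discussed. The protocol describes one interventionist per site as each participant's single point of contact, so any criticism points at an identifiable person.

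The expected error runs one way, towards approval. Aim 3 is meant to find what worked less well, so lost criticism is the costly kind of loss. It also happens when the question is answered, before any analytic safeguard can act. At stake is how useful the Veteran interviews are for revising EnCoRE before an implementation trial.

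**Working it through.** The plan states no figure on this point, so there is nothing to reproduce. The check is to set the statements side by side and look for anything that separates the interviewer from supervision of delivery.

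**1. Is the PI a permitted interviewer of Veterans?** Yes. The list is one PI + one Co-I + two coordinators + two research assistants = 6 people. It is not split between Veteran and provider interviews, so the text neither assigns Veterans to the PI nor bars the PI from interviewing them.

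**2. Do the Veteran interviews ask about the interventionist?** Yes, expressly (Data Collection).

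**3. Does the PI supervise the interventionists?** Yes (Risks to Participants). For the others on the list the text shows no such role. Data Collection has the PI and co-investigators supervise the assessments, but that is not supervision of treatment delivery. The supervisory conflict is therefore documented for the PI alone.

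**4. Do the provider interviews raise the same problem?** No. Providers are asked about treating these Veterans, about EnCoRE's content and processes, and about its fit with other care. They are not asked what the interventionist could have done better.

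**5. Do the existing safeguards reach the problem?**

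| Safeguard | Where | What it protects |
|---|---|---|
| Private rooms | Section 7 | Privacy |
| Audio recording, outside transcription | Data Collection; sections 5.6 and 7 | Accurate capture |
| Two coders, consensus, no preset template | Section 5.6 | Interpretation |

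None of these bears on what a Veteran is willing to say to the interventionist's supervisor.

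**6. How many interviews could be affected?** Section 5.6 plans 49 Veteran interviews, and the PI's share is not stated. The range is 0 to 49. If all six people shared the work equally, which is an assumption and not in the documents, the PI would do 49 / 6 = 8.2, about 8. The amount of criticism lost per interview cannot be derived.

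**7. Who could do the interviews instead?** Only EnCoRE Veterans are interviewed, so conducting the interview reveals the arm. Research assistants are listed as interviewers and, in the same section, as the collectors of assessment data. An unconditional transfer to them would trade one problem for another. Whether the coordinators deliver, supervise or rate anything is not stated.

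**The case against.** The strongest reply is that the text shows only a possibility. The PI may take provider interviews only, in which case no Veteran is affected. The mechanism also needs the Veteran to know that the interviewer supervises the interventionist, and nothing says that Veterans are told. The supervision is described in a section on participant risk and concerns clinical issues. Any study-team interviewer might attract polite answers, and the documents give no measure of what the PI's presence adds. Criticism has other outlets: satisfaction questionnaires at post-treatment and follow-up, attendance and outreach tracking, and interventionist logs and supervision notes. Finally, sections 1.0 and 4.0, which deal with personnel, and the consent pages were not in the text available for this review. An allocation of duties may stand there.

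Much of this stands, and it limits the point. A reader might infer four stronger things that the documents do not support:

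- That Veterans are in fact interviewed by the supervisor. The text permits this but does not say that it happens.
- That the provider interviews share the conflict. Their questions do not concern the interventionist's performance.
- That the coordinators are known to be suitable replacements. Their other duties are not described.
- That de-identified transcripts would protect the Veteran's candour about the interventionist. With one interventionist per site, hiding the Veteran's name would not hide who is being criticised.

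What does not stand is the suggestion that other sources make the matter moot. Logs and supervision notes come from the delivery side, and questionnaires do not replace a Veteran's own account in an open interview. The possibility is also easy to close.

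**Conclusion.** The point holds as a design weakness of limited reach. The protocol permits the interventionists' supervisor to ask EnCoRE Veterans what the interventionist could have done better. If that happens, some of the criticism that Aim 3 is meant to gather may not be voiced. Between 0 and 49 interviews are exposed, and the size of the effect is unknown.

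The conclusion rests on two assumptions. One is that a supervisor's presence discourages criticism, which is a methodological inference and not something that the documents state. The other is that the personnel sections do not already keep the PI out of these interviews. If they do, the point falls away.

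It concerns Aim 3 only. The primary comparison, the sample size of 108 and the quantitative inference are untouched. This is a worthwhile improvement, not an error that has to be corrected.

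**What to change.** In Data Collection, state that the PI, and anyone who delivers or supervises EnCoRE, will not conduct Veteran interviews, and that the remaining listed staff will. Among these, prefer someone who will not rate that Veteran's later outcomes, because the interview reveals the arm. Check the coordinators' and research assistants' duties, and the personnel sections, before naming anyone.

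Record the interviewer on each transcript, so that themes can be compared by interviewer. The PI and Co-I can keep their part in the analysis, and the provider interviews need no change on this ground.

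The SAP is dated April 2021 and written in the past tense, so the interviews may already be complete. In that case, report who conducted each one and compare the themes, especially critical ones, between PI-led and other interviews.

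The cost is a few lines of protocol text and reassignment within the existing list, with less flexibility in scheduling. If no listed person turns out to be free of delivery, supervision and outcome rating, excluding the PI and those who deliver or supervise EnCoRE comes first. The outcome-rating condition is a preference.

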### Protection of Vulnerable Populations- Mentally III

Staff is trained to recognize symptoms of SMI and cognitive impairment that could undermine the ability to provide informed consent. Since some participants have poor reading skills, the consent form will be reviewed aloud to all participants in tandem with their own silent reading of the document. The study staff member will review any points about which the potential participant is unclear, and the participant will be invited to ask questions as needed. Staff is trained in strategies for interacting with people with SMI, including speaking slowly and

clearly, stopping frequently to summarize, and providing time for questions. After reading the consent, and before obtaining a signature, a brief questionnaire is administered to verify that the participant has understood the consent document. This questionnaire is attached to the consent form and is completed immediately after explaining the informed consent form and before obtaining the participant's signature. If the participant is unable to answer the questions correctly, the research assistant reviews the aspects of the study that the participant did not understand and asks the questions again. If the participant cannot answer all questions correctly, he/she will not be enrolled.

#### Protection of Vulnerable Populations-Employees

There will be no specific risks associated with study participation for Employees or Lab Personnel. Informed consent will be obtained and research assessments conducted in the same manner as for other participants. All potential participants will be told that their employment status will not be affected by their decision to participate in the study or not.

## **5.2 Recruitment Methods**

### Recruitment of Schizophrenia Participants:

We will first recruit and assess approximately 6 Veterans with schizophrenia from one study site to participate in a training trial. We will implement EnCoRE and the control condition, videotape sessions, and provide in-depth supervision and feedback. We will refine the EnCoRE manual for the RCT based on interventionist training and feedback. Following refinement of the treatment manual, we will then recruit a randomized control trial with 108 veterans with Schizophrenia.

Potential veteran participants will be identified by several methods: (1) CPRS chart review and screening via use of partial HIPAA waiver, (2) VA clinician referrals of participants who meet inclusion criteria and who might be interested in participating, (3) Self referrals by participants who hear about the study and are interested in participating, (4) Self-referral via IRB approved study flyer, (5) Self-referral via IRB approved announcements in the MIRECC newsletter which is generated on a quarterly basis. We will also use the VAMHCS MIRECC Recruitment Database (Protocol # 00042721) at the Baltimore and Perry Point sites to identify participants who meet study eligibility criteria. We will also provide an IRB approved study flyer to other MIRECC study teams to distribute to Veterans participating in other studies; Veterans who receive the flyer this way can self-refer to this study if they are interested.

Participants will be screened for eligibility via chart review. Study staff will then contact a VA treatment team member to determine if a potentially eligible participant is clinically stable enough to participate in the study and can be contacted for recruitment. If the VA treatment team member does not respond within one week the study team will accept this as an implied approval and recruitment will proceed. Per VA CIRB requirements, initial contact with Veterans

will be made in person or by letter prior to any telephone contact. In-person contact will be made with Veterans before or after their VA appointments.

We may also send out a recruitment letter to potential participants to see if they are interested in participating in the study. They will be given contact information for the study team as well as a postcard to mail back in a sealed pre-stamped envelope to indicate their interest or lack of interest in the study. A follow-up phone call will be made after one week to ensure the participant received the mailing, and to provide them with additional information about the study if they express an interest.

Recruitment will involve the following process:

- 1) Participants will be screened for preliminary eligibility via chart review.
- 2) For those who meet preliminary eligibility criteria, study staff will contact a member of the Veteran's VA mental health treatment team to determine if the Veteran is clinically stable enough to participate in the study and can be contacted for recruitment.
- 3) For those who are identified as sufficiently clinically stable, a form describing the study will be provided to the treatment team member to give to the Veteran at his/her next appointment. This form will include study team contact information and describe that the Veteran may be approached by the study team about his/her participation.
- 4) If the Veteran has any objections to being approached by the study team, this will be recorded on the form and the form will be returned to the study team.
- 5) If the Veteran is not scheduled to see the treatment team member within 2 weeks, a letter will be sent to the Veteran as outlined above. A second letter will be sent if we have not heard back from and were unable to reach a Veteran after sending the first recruitment letter. This would be useful in cases in which a Veteran does not receive the first letter. If a Veteran does not respond after two letters, we will not send additional letters.

Further, it should be re-iterated that research assistants who will interact with participants are all specially trained to work with persons with serious mental illnesses. Research staff will first consult the participant's treatment team for permission to begin the consent process. This will help avoid approaching people who may be in crisis or may not be able to comprehend the study procedures, risks, and benefits.

